Each participant should be scanned using the same machine throughout the study. In case of machine change, or hardware/software upgrade the necessity to complete another test scan using the new equipment should be agreed upon with the central imaging core lab.

8.1.2	Disability Assessments					
8.1.2.1	Expanded	Disability	Status	Scale/	CCI	
CCI						

The EDSS is a neurological assessment to evaluate disability in neurologic deficient patients with MS. It will be completed by the evaluating physician, who evaluates the participant's state according to the KFS Grades. The repeated application allows the measurement of the level of disability over time (Kurtzke 1983).

An EDSS progression is defined as an increase in the EDSS scale as follows:

- If the Baseline* EDSS score is 0, the increase must be > 1.5 units
- If the Baseline* EDSS score is ≥ 0.5 or ≤ 4.5 , the increase must be ≥ 1.0 units
- If the Baseline* EDSS score > 5.0 the increase must be > 0.5 units

Sustained EDSS progression is defined as EDSS progression (as defined above) confirmed by subsequent measurements of at least 3 months apart.

*The extension study-specific starting point for analyses is the parent study baseline (before the initial dose of cladribine tablets).

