9.1 Definition of Baseline and Change from Baseline

The Baseline is defined as the MAGNIFY MS Baseline (parent study Baseline) that is specified in Section 9 of MAGNIFY MS IAP version 3.0, unless otherwise specified.

Absolute and percent changes from baseline are defined as:

- Absolute change = Visit value Baseline value
- Percent change = 100 * (Visit value Baseline value) / Baseline value

The Percentage Change from Baseline will be set to missing for participants with a zero at Baseline.

All changes that are defined as comparing to prior initial dose of cladribine tablets will use the MAGNIFY MS Baseline as reference.

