9.6 Study Period

Study Periods

The following study periods are defined:

Treatment Period (i.e., Parent Study Period): see MAGNIFY MS IAP version 3.0 for definition.

Course 1 Treatment Period: see MAGNIFY MS IAP version 3.0 for definition.

Course 2 Treatment Period: see MAGNIFY MS IAP version 3.0 for definition.

Gap Period:

- Start = Visit end date of M24 Visit + 1
- End = Extension Study Baseline Visit start date

Year 3 Visit Period:

- Start = Visit end date of M24 Visit + 1
- End = Visit end date of M36 Visit

Year 4 Visit Period:

- Start = Visit end date of M36 Visit + 1
- End = Visit end date of M48 Visit

Year 3 Visit and Year 4 Visit Period (i.e., **Extension Study Period**):

- Start = Visit end date of M24 Visit + 1
- End = Visit end date of M48 Visit

After start of study medication until end of Year 3 Visit Period:

- Start = Start of study medication (see MAGNIFY MS IAP version 3.0 for definition)
- End = Visit end date of M36 Visit

After start of study medication until end of Year 4 Visit Period (i.e., **Parent and Extension Study Period**):

- Start = Start of study medication (see MAGNIFY MS IAP version 3.0 for definition)
- End = Visit end date of M48 Visit

In case of missing M48 Visit or early discontinuation before an End of Period defined above, the Visit end date of EW Visit will be used to replace the corresponding End date, or the study discontinuation date will be used if the EW visit was not performed.

In case of missing M36 Visit, the Visit end date of M36 Visit in the above definitions (including Start and End) will be replaced by MAGNIFY MS M24 Visit date + 480 days (which is obtained by 360 (12 months) + 90 (3 months delay allowed for FAS) + 30 (Visit window)), or the Visit end date of EW Visit if earlier, or date of discontinuation if earlier and the EW Visit was not performed.

Study Periods for MRI Assessments

The MRI scans in the parent study were reconciled during central MRI review process. Therefore, MRIs were considered as Baseline MRIs if assigned to the Baseline Visit by the central imaging review.

The following study periods for MRI assessments are defined as per MAGNIFY MS IAP version 3.0 with extension to Month 36 Visit and Month 48 Visit MRI scans:

Baseline Period (p₀): The Baseline Period is defined as the Period between the Screening and the Baseline MRI scan in MAGNIFY MS trial.

Post-Baseline Periods (ppost-Baseline):

Yearly Periods:

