14.1.1 Primary Objective: Derivation and analysis of the primary endpoint

No Evidence of Disease activity (NEDA), also referred to as freedom from disease activity, is a new goal that is emerging in MS treatment. NEDA is a composite measure of disease activity, including relapses, cognition and disability progression, and MRI activity.

NEDA-3 during the Extension Study Period is defined as absence of the following three events during the Period:

- Qualifying Relapses
- 6-months Confirmed Disability Progression (6MCDP, see definition below)
- MRI Activity (i.e., presence of T1 Gd+ lesions and/or active T2 lesions)

NEDA-3 will be analyzed with the Kaplan-Meier (KM) time-to-event method to reduce the impact of unknown/missing information.

The start date will be the end date of M24 Visit + 1.

The event date will be defined as the minimum of

- the onset date of the first qualifying relapses during the Extension Study Period
- the start date of the first 6MCDP during the Extension Study Period (see definition below)
- the scan date of the first MRI during the Extension Study Period where at least one T1 Gd+ lesion or at least one active T2 lesion (see Section 9.8 for definition) is identified.

Imputation of partial onset dates of relapses is described in Section 9.7. Since full dates of MRI scan and EDSS assessment are mandatory, partial dates of 6MCDP, or MRI Activity are not expected.

If the participant did not experience any of the three events described above during the Extension Study Period, the minimum of the scan date of the last available MRI, the assessment date of the last available EDSS, and the Extension Study completion/discontinuation date will be used as the censoring date.

The time to disease activity (in months) will be calculated as [event date or censoring date as applicable – start date + 1]/30.4375. The number of participants at risk, failed, and survival rate (i.e., the proportion of participants with NEDA-3) along with the 95% CI will be estimated as per the KM method and reported at 6-months intervals. The KM survival curve will be plotted as well.

A descriptive summary of number and proportion of participants with event (overall and by type of event, i.e., qualifying relapse, 6MCDP, or MRI activity as the earliest event) and censored will be also presented.

6MCDP

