The 6MCDP during Extension Study Period is defined as sustained increase in EDSS score that started during the Period. A Sustained Increase in EDSS score is defined by an increase of:

- at least 1.5 points if the Baseline EDSS score was 0, or
- at least 1 point if Baseline EDSS score was between 0.5 and 4.5 inclusively, or
- at least 0.5 point if the Baseline EDSS score was at least 5,

that occurs over a 6-months' time-period.

The increase will be defined as sustained when it occurs on two post-Baseline Visits during the Extension Study Period that are at least 166 days apart (to be consistent with the parent study minimum visit gap) and no observations at any other visits (including unscheduled visits) in between are less than the defined increase. The assessment date of the earlier of the two EDSS assessments with the defined increase will be defined as the start date of 6MCDP.

For descriptive summaries the following rules will be defined:

Qualifying Relapse

- Yes: any qualifying relapse reported during the Extension Study Period,
- No: Extension study period completed, and no qualifying relapse reported during the Extension Study Period,
- Unknown: otherwise.

6MCDP

• Yes: sustained increase in EDSS score that started during the Extension Study Period,

- No: at least 2 post-Baseline EDSS assessments that are 166 (or more) apart and no sustained EDSS progression that started during the Extension Study Period,
- Unknown: Otherwise.

MRI activity

- Yes: any T1-Gd+ or active T2 observed during the Extension Study Period,
- No: at least one post-Baseline MRI and no T1-Gd+ or active T2 observed during the Extension Study Period,
- Unknown: otherwise.

Analysis (Analysis Set)	Derivation	Statistical Analysis Methods	Missing data handling		
	Primary endpoint: Proportion of participants with NEDA-3 during Year 3 Visit and Year 4 Visit Period after the initial dose of cladribine tablets				

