14.2.3 Time to MRI Activities, 6MCDP, Qualifying Relapse and Treatment Start with Other DMDs

Time (in months) from the initial dose of cladribine tablets (i.e. start date = date of Day 1 as defined in Section 9.5) to the following events will be calculated as [event date or censoring date as applicable – start date + 1]/30.4375, and analyzed similarly as in Section 14.2.2 using the KM method.

- first new or enlarging T2 lesion
 - Event date: the scan date of the first MRI during the Parent and Extension Study Period where at least one active T2 lesion (see Section 9.8 for definition) is identified
 - Censoring date: participants with no active T2 lesion identified at any scans during the Parent and Extension Study Period will be censored at the scan date of the last available MRI during this Period
- first new T1 Gd+ lesion
 - Event date: the scan date of the first MRI during the Parent and Extension Study Period where at least one new T1 Gd+ lesion (see Section 9.8 for definition) is identified
 - Censoring date: participants with no new T1 Gd+ lesion identified at any scans during the Parent and Extension Study Period will be censored at the scan date of the last available MRI during this Period
- first 6MCDP, as measured by EDSS
 - Event date: the start date of the first 6MCDP during the Parent and Extension Study Period
 - 6MCDP during the Parent and Extension Study Period will be defined similarly as in Section 14.1.1 with just Extension Study Period replaced by Parent and Extension Study Period.
 - Censoring date: participants with no 6MCDP started during the Parent and Extension Study Period will be censored at the assessment date of the last available EDSS during this Period
- first qualifying relapse
 - Event date: the onset date of the first qualifying relapse during the Parent and Extension Study Period

 Censoring date: participants with no qualifying relapse reported during the Parent and Extension Study Period will be censored at the Extension Study completion/discontinuation date

Time (in months) from M24 Visit (i.e. start date = end date of M24 Visit + 1) to the following events will be calculated as (event date or censoring date as applicable – start date + 1/30.4375, and analyzed similarly as in Section 14.2.2 using the KM method.

- first new or enlarging T2 lesion
 - Event date: the scan date of the first MRI during the Extension Study Period where at least one active T2 lesion (see Section 9.8 for definition) is identified

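### SAP 14.1.1 lets an EDSS increase already present at M24 count as a Year 3–4 progression, because its start-date rule makes the in-period onset condition true automatically

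*SAP*

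**What the plan says.** The primary endpoint is the Kaplan-Meier proportion with NEDA-3 over the Extension Study Period, and 6MCDP is its disability component. SAP 14.1.1 opens the definition with an onset condition: "The 6MCDP during Extension Study Period is defined as sustained increase in EDSS score that started during the Period". The Yes and No categories for the descriptive summaries repeat it. SAP 9.6 defines the period by "Start = Visit end date of M24 Visit + 1".

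The operational rule follows. The increase is at least 1.5 points from a Baseline score of 0, 1 point from 0.5–4.5, or 0.5 point from 5 upwards. Baseline is the parent-study Baseline (SAP 9.1; Protocol 8.1.2.1). The increase counts as "sustained when it occurs on two post-Baseline Visits during the Extension Study Period that are at least 166 days apart", provided no score in between falls below the threshold. Onset is then set by this sentence: "The assessment date of the earlier of the two EDSS assessments with the defined increase will be defined as the start date of 6MCDP". That date is one of the three candidates whose minimum is the primary event date.

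For the analysis from first dose, SAP 14.2.3 says "6MCDP during the Parent and Extension Study Period will be defined similarly as in Section 14.1.1 with just Extension Study Period replaced by" the combined parent and extension period. SAP 11.3 adds that EDSS scores of participants with a gap period between the studies still count towards progression.

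**The concern.** The M24 score lies one day outside the period. It cannot be one of the two qualifying assessments, and it cannot lie between them. An increase that was complete by M24 and simply persists is therefore dated to the first in-period EDSS and counted as new.

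The other NEDA-3 components do not work this way. A relapse must have its onset in the period. T2 activity is new or enlarging since the preceding scan. SAP Section 7 treats Gd+ lesions at the yearly scans as new. Only disability can register a change that was finished before time zero. Eligibility (Protocol 5.1) does not exclude participants who progressed in the parent study, so such cases can enter.

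The primary estimate is meant to describe activity after M24. The same rule also feeds Year 3 Visit Period NEDA-3 (SAP 14.2.1), time from M24 to first disease activity (14.2.2) and time from M24 to 6MCDP (14.2.3). The robustness analyses in 14.1.2 reuse the derivation, so none of them would reveal the effect.

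**Working it through.** **Inputs.** The thresholds, the 166-day rule and the start-date rule come from SAP 14.1.1. The period start is from SAP 9.6. Visits 1 and 2 fall at 360 and 720 days after M24 (SAP 9.5). Time in months is (event date − start date + 1)/30.4375. The protocol synopsis gives 200–220 evaluable participants. The plan states no figure on this point to reproduce.

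**Step 1: apply the rules to example EDSS series.** Scores are Baseline/M24/M36/M48 and days are counted from M24. The look-back column is the rule proposed under fix, without any further-step option.

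| Series | SAP 14.1.1 as written | SAP 14.2.3 (from first dose) | Look-back |
|---|---|---|---|
| A: 2.0/3.0/3.0/3.0 | day 360 | M24 or earlier | none |
| E: as A, plus gap-period EDSS 3.0 at day 90 | day 90 | M24 or earlier | none |
| C: 2.0/2.5/3.0/3.0 | day 360 | day 360 | day 360 |
| F: 2.0/3.0/3.0/2.0 | none | M24 or earlier | none |
| T: as A, plus gap-period EDSS 2.0 at day 90 | day 360 | day 360 | day 360 |
| T0: as T, but the day-90 dip is not recorded | day 360 | M24 or earlier | none |
| D: 2.0/3.0/4.0/4.0 | day 360 | M24 or earlier | none (day 360 with a further-step option) |
| H: 2.0/3.0/3.5/3.5 | day 360 | M24 or earlier | none |

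Day 360 is (360 − 1 + 1)/30.4375 = 11.83 months. Day 90 is 90/30.4375 = 2.96 months.

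In A and E nothing changed after M24, yet the primary analysis records an event, and the two sections give one increase two onset dates. F shows that carry-over needs the increase to persist at two in-period assessments. C and T show that a look-back keeps a genuine later onset.

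**Step 2: size, under assumptions.** Let q be the share of participants whose increase is present at M24 and persists at two in-period visits at least 166 days apart. Let p be NEDA-3 without the artefact. Neither is in the documents. If the two are independent, the estimate becomes p(1 − q), a fall of q × p.

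| q | p | Fall (points) |
|---|---|---|
| 1% | 50% | 0.5 |
| 1% | 70% | 0.7 |
| 3% | 50% | 1.5 |
| 5% | 70% | 3.5 |

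In participants: 200 × 0.01 × 0.50 = 1.0 up to 220 × 0.05 × 0.70 = 7.7.

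A simulated Kaplan-Meier analysis (200,000 participants, no dropout) gave 1.51 points for q = 3%, p = 50% and 3.54 for q = 5%, p = 70%. With an assumed 10% dropout after M36 these became 1.32 and 3.10.

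The 95% half-width is 1.96 × √(p(1 − p)/n): 6.93 points for p = 0.5, n = 200 and 6.06 for p = 0.7, n = 220. The largest fall in the table is 3.5/6.06 = 58% of that half-width. Wider assumptions give more: 10% carry-over with p = 80% gives 8.0 points, against a half-width of 5.54 at n = 200.

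**Step 3: direction of the change.** The look-back adds a condition to the existing rule, so it can remove or delay extension-period events but cannot create or advance one. A check of 3,360,000 EDSS patterns, with a further-step option included, found no added or advanced event. The change can therefore only raise NEDA-3.

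**The case against.** The strongest reply is that the onset wording is itself a separate test, repeated in the Yes and No rules, and that a careful programmer would exclude carried-over increases. That is possible. But the only sentence that assigns an onset date satisfies the test automatically, and no text says how to establish an earlier onset. Two programmers could produce different primary results.

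A second reply is that parent Baseline is a stated choice, and that being confirmed worse than before treatment during Years 3–4 is a legitimate estimand. The choice of reference stands and need not change. Reference score and onset date are separate matters, and if prevalent progression is intended the onset wording is wrong.

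Third, resetting the reference to M24 for participants already raised would put two references into one endpoint. This also stands, and such a step should not be imposed on the primary definition.

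Fourth, there is some visibility elsewhere: the first-dose analyses date these increases correctly, SAP 14 plans by-visit EDSS changes, and redacted sections may hold more. None of the visible outputs gives the number of 6MCDP events already present at M24.

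A reader might also infer more than the documents support:

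- That the sentences flatly contradict each other. They do not: the second makes the first empty.
- That the rule ignores all earlier EDSS. It uses the parent Baseline; what it disregards is every post-Baseline score up to and including M24.
- That Year 4 Visit Period NEDA-3 is inflated with events in the same way. SAP 14.2.1 takes its event date from 14.1.1, where the first 6MCDP of a carried-over increase normally falls at or before M36, so an effect there is not clear.

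**Conclusion.** The point holds for the rule as written. An increase over parent Baseline that is present at M24 and persists at two in-period visits at least 166 days apart enters the primary endpoint as a Year 3–4 event, while SAP 14.2.3 dates the same increase to M24 or earlier. The direction is known: extension-period NEDA-3 is understated, so the error works against the product.

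The size is not known. The 0.5–3.5 point range rests on assumed values of q and p and on their independence, and it shrinks if carriers also have more relapse or MRI activity. The documents do not show what was programmed, so confidence attaches to the text and not to a count of misclassified participants. The study tests no formal hypothesis, but a one-directional shift in the primary estimate is worth correcting.

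**What to change.** In SAP 14.1.1:

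- Keep parent Baseline as the reference.
- Define onset as the first EDSS in the uninterrupted run of scores meeting the threshold, across the full post-Baseline series including M24 and any gap-period scores. SAP 14.2.3 in effect already does this.
- Count an extension-period 6MCDP only if that onset falls after the M24 visit end date.
- Report how many participants meet the threshold at M24, show the primary result under the present rule alongside, and list the change in SAP Section 7. The first-dose analyses stay as they are.
- Pre-specify how further worsening is handled in participants already raised at M24 (cases D and H). A further threshold step from the M24 score could be offered as an option or sensitivity analysis; it would recover D but not H.

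If prevalent progression is meant to count, say so, remove the onset wording, and still report the M24 count and the look-back result as a sensitivity analysis.

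The data cost is small, since Protocol 5.1 requires an M24 EDSS for eligibility. There are three real costs. An increase first seen at M24 and confirmed only in the extension counts only in the first-dose analyses. A single transient M24 score can cancel a true later progression when no EDSS lies between M24 and M36 (case T0). And the change can only raise NEDA-3, in an open-label study with investigator-rated EDSS and an SAP version dated 05 Oct 2023, when last visits were planned for Q4 2023. That is why both versions should be shown.

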9.8 Data Handling for MRI data

MRI data will be integrated with MRI data from the MAGNIFY MS trial, which will be handled according to "Data Handling for MRI data – Data handling of Tertiary endpoints" in Section 9 of the MAGNIFY MS IAP version 3.0.

The MRIs will be evaluated by independent central review. The assignment of MRIs to the respective Visits in the parent study was ensured by the central reading process, while this process is not adopted in the Extension Study. Therefore, the statistical analysis will be based on the MRI Visit assignments as provided by central reading for parent study data and MRI Visit assignments as reported in the eCRF for Extension Study data. A 6-months window will be allowed for the Extension Study MRI data. An MRI assessment will be excluded from all analyses if the absolute value of (MRI assessment date – Visit date) > 185 days (which is obtained by 180 [6 months] + 5 [window allowed by protocol]).

All derived lesion counts (except for the Mean T1 Gd+ lesion count) as specified below will be classified as Not Evaluable (NE) if one of the components required for the calculation has been classified as NE by the central reading. The Mean T1 Gd+ lesion count will be set to NE only, if all T1 Gd+ lesion counts that correspond to the respective Period are classified as NE. In all other cases the mean will be calculated based on the available counts during the respective Period.

For definition of Period see Section 9.6 "Study Periods for MRI Assessments".

T1 Gd+ lesion count

- The T1 Gd+ are defined as follow: T1 Gd+ lesion count (by Visit) = T1 Gd+ lesions count from the MRI at the respective Visit.
- Mean T1 Gd+ lesion count (by Period) = sum of all T1 Gd+ lesion counts during the Period /# of scans belonging to the respective Period with non-missing T1 Gd+ lesion count.

All MRI scans belonging to a Period are MRI scans that have been performed during the Period including start and end Visits. For post-Baseline periods starting at Baseline, the Baseline Visit will not be included. For example, Period 48.1 will include all MRI scans during both MAGNIFY MS trial and Extension Study except Screening and Baseline Visit.

- New T1 Gd+ lesion count (by Period)
 - For Periods including up to Month 24 Visit, refer to "Data handling for MRI data: Data handling of Tertiary endpoints" in Section 9 of MAGNIFY MS IAP version 3.0
 - For other Periods ending at Month 36 / Month 48 Visit,

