10.2.2 Reasons Leading to the Exclusion from an Analysis Set

A frequency table, as well as a listing, organized according to reasons for exclusion from the FAS and TCS, respectively, will be provided, if applicable.

Possible reasons for exclusion from the FAS include:

- Not fulfill any of the inclusion criteria
 - o Participants of the MAGNIFY MS trial who received at least a single dose of cladribine tablets during the MAGNIFY MS trial
 - O Data on MRI is available/acquired from at least parent study Month 18 or Month 24 visit
 - o Data on EDSS and relapse is available/acquired from parent study Month 24 visit
 - o Capable of giving signed informed consent
- Meet any of the exclusion criteria
 - o Participant is considered by the Investigator, for any reason, to be an unsuitable candidate for the study
 - Participation in other studies/trials

Possible reasons for exclusion from the TCS include:

- Participants are not included in the FAS
- Participants did not complete the full treatment course of the first and second year in the parent study

11 Demographics and Other Baseline Characteristics

If not stated otherwise, the following analyses will be performed based on the FAS.

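### As written, a participant with no extension MRI is scored free of MRI activity, so the MRI *Unknown* category is empty; the 6MCDP *No* rule has the same gap

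*SAP*

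**What the plan says.** SAP 14.1.1 gives *Yes*/*No*/*Unknown* rules for the descriptive summaries of the three NEDA-3 components over the Extension Study Period.

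- MRI activity: "No: at least one post-Baseline MRI and no T1-Gd+ or active T2 observed during the Extension Study Period"; anything that is neither *Yes* nor *No* is *Unknown*.
- 6MCDP: *No* requires "at least 2 post-Baseline EDSS assessments that are 166 (or more) apart" (the unit is missing) and no sustained progression that began in the period.
- Relapse: *No* requires that the participant completed the period.

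The 6MCDP event definition in the same section is narrower. An increase is sustained when "it occurs on two post-Baseline Visits during the Extension Study Period that are at least 166 days apart".

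Four other provisions fix what these rules mean.

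- SAP 9.1, on Baseline: "The Baseline is defined as the MAGNIFY MS Baseline (parent study Baseline"), unless stated otherwise. Section 14.1.1 does not state otherwise.
- SAP 9.8, on a post-Baseline MRI period: "Period 48.1 will include all MRI scans during both MAGNIFY MS trial and Extension Study except Screening and Baseline Visit".
- SAP 10.2.2, following inclusion criterion 1, on eligibility: "Data on MRI is available/acquired from at least parent study Month 18 or Month 24 visit".
- SAP 9.6, on the Extension Study Period: "Start = Visit end date of M24 Visit + 1".

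SAP 14.1.2 then lists a crude summary of the components and of NEDA as a sensitivity analysis on the FAS, with missing values shown as their own category.

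**The concern.** Neither *No* rule requires that the scan or the EDSS pair come from the period being scored. Parent-study data can satisfy both. A participant about whom nothing was learned on MRI during the extension is then reported as lesion-free.

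Of the sensitivity rows in SAP 14.1.2, the crude summary is the only one that handles missing data differently from the primary analysis. Its purpose is to let a reader see how much of the event-free percentage was observed. For MRI it cannot do that, because its missing category is empty by construction.

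The effect can carry into crude NEDA. This SAP does not say how the three components combine. If all three must be *No*, the relapse rule keeps early leavers out, but a participant who completes follow-up and misses both extension scans would still count as NEDA-3.

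**Working it through.** The plan states no figure on this point, so there is nothing to reproduce. The check has three steps.

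**1. MRI rule.** Eligibility guarantees a Month 18 or Month 24 scan, and the FAS contains only eligible participants. The period starts the day after the M24 Visit ends, so that qualifying scan lies outside it but is post-Baseline. The possible FAS patterns are:

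| Usable extension scan | Lesion in the extension | As written | In-period scan required |
|---|---|---|---|
| None | not observable | *No* | *Unknown* |
| At least one | none | *No* | *No* |
| At least one | one or more | *Yes* | *Yes* |

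*Unknown* would need no post-Baseline scan at all, which eligibility rules out. The first row also covers a participant whose only extension scan is removed under SAP 9.8: "An MRI assessment will be excluded from all analyses if the absolute value of" the difference between scan date and visit date is above 185 days.

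**2. 6MCDP rule.** Visit 1 is planned 360 ± 30 = 330 to 390 days after M24, well above 166. Eligibility guarantees the M24 EDSS. With no sustained increase:

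| EDSS available | As written | In-period pair required |
|---|---|---|
| M24 only | *Unknown* | *Unknown* |
| M18 and M24 (assumed about 180 days apart) | *No* | *Unknown* |
| M24 and Visit 1 | *No* | *Unknown* |
| M24, Visit 1 and Visit 2 | *No* | *No* |

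In the third row *Yes* was impossible, because the event definition needs two assessments inside the period and there is only one. Unlike MRI, 6MCDP *Unknown* is not necessarily empty. The documents do not show that every participant has a qualifying pair from the parent study.

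**3. Size for MRI.** Let m be the share of the FAS without a usable extension scan and p the true share with MRI activity, assumed equal in those with and without a scan. Both are assumptions; the documents give neither.

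- As written: *No* = (1 − m)(1 − p) + m, *Unknown* = 0, *Yes* = (1 − m)p.
- Corrected: *No* = (1 − m)(1 − p), *Unknown* = m, *Yes* = (1 − m)p.
- Overstatement of the MRI-free percentage against the truth: (1 − m)(1 − p) + m − (1 − p) = m × p.

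| m | p = 10% | p = 30% | p = 50% |
|---|---|---|---|
| 2% | 0.2 points | 0.6 | 1.0 |
| 5% | 0.5 | 1.5 | 2.5 |
| 10% | 1.0 | 3.0 | 5.0 |

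Example with m = 5% and p = 30%:

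- As written, *No* = 0.95 × 0.70 + 0.05 = 71.5%, *Unknown* 0%, *Yes* 28.5%.
- Corrected, *No* = 66.5%, *Unknown* 5.0%, *Yes* 28.5%.
- Among those with known status, 66.5 / 95 = 70.0% are free of activity, which equals the assumed truth.

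Five per cent is 10 to 11 people among the 200 to 220 evaluable participants planned, or about 13 at the enrolment maximum of 256.

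**The case against.** The best counter-argument is about reading. The closing period phrase of the MRI *No* rule could govern the whole line, scan included. The rules sit in a section about the Extension Study Period, SAP 9.7 analyses data as observed, SAP 9 puts missing observations in a separate category, and an *Unknown* level exists. That reading is possible but weaker. The phrase repeats the lesion wording of the *Yes* rule. The 6MCDP event definition names the period explicitly when it restricts the visits. The Course 1 and Course 2 rules in SAP 14.2.1 require available T1 Gd+ and active T2 values from the period scored. Nor can the reading rescue the 6MCDP *No* rule, whose period phrase attaches to when progression started.

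A second argument is that little output changes. *Yes* counts and the Kaplan-Meier estimate stand, and missingness can also be seen in numbers at risk, censoring counts, by-visit tables and discontinuations. This is true and limits the importance of the point, but none of those tables corrects the crude MRI and NEDA percentages.

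Third, m may be small. The Early Withdrawal visit includes an MRI and is mapped to a missing planned visit. However, Protocol 4.1 allows a telephone call in place of that visit, so m need not be zero.

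Two limits of the remedy also stand. A single Month 36 scan would still support *No* for both years. For the crude rows that start at study medication, parent scans lie inside the period, so the MRI result there barely changes. Both match the standard the SAP itself uses for Courses 1 and 2. A composite rule may exist in the parent-study analysis plan to which SAP 14.2.1 refers, but that plan is not available here.

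**Conclusion.** The concern holds. Followed as written, the MRI rule turns an absent extension scan into a *No* for every such FAS participant and leaves *Unknown* empty. The 6MCDP rule can return *No* where the data could never have produced *Yes*. The displayed MRI *No* percentage is too high by m points, and the MRI-free percentage is overstated against the truth by m × p: 0.2 to 5.0 points for m of 2% to 10% and p of 10% to 50%. These sizes rest on assumed m and p, and on equal activity in scanned and unscanned participants. The effect on crude NEDA-3 cannot be sized, because the combining rule is not given. The problem is confined to the descriptive summaries and should be fixed before the crude table is produced.

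**What to change.** In SAP 14.1.1, for the Extension Study Period:

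- **MRI *No*:** at least one MRI inside the period with evaluable T1 Gd+ and active T2 counts, and none positive. Otherwise *Unknown*, unless *Yes*.
- **6MCDP *No*:** at least two EDSS assessments inside the period, at least 166 days apart (add the unit), and no sustained increase that started in it. Otherwise *Unknown*, unless *Yes*.
- **Crude NEDA-3:** met only if all three components are *No*; not met if any is *Yes*; *Unknown* if none is *Yes* and at least one is *Unknown*.

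For the crude rows in SAP 14.2.1 that start at study medication, tie the required MRI and EDSS to the period being scored, as the Course 1 and Course 2 rules already do for MRI.

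The cost is SAP wording and derivation code; no new data are needed. The downside is that more participants appear as *Unknown* and the crude MRI-free and progression-free percentages fall, MRI-free by m points.
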